All measured variables will be assessed for distributional qualities and transformed if necessary for use in the selected statistical models. Adequacy of random assignment and matching will be tested using t-tests and chi-square tests as appropriate. All pre-classification variables (age, BMI, insomnia, medical comorbidity, prior depression history) and baseline values of outcomes will be compared; those that are significantly different between females and males (at $P < 0.15$) will be considered for inclusion as covariates in the main analyses. Missing data patterns will be analyzed to assess the potential for biased parameter estimates; missing data will not be imputed as the methods selected allow for missing data under common missingness assumptions. The basic design for Aim 1 is a 2 group (females vs. males) by 2 condition (endotoxin vs. placebo) independent balanced analysis of variance (ANOVA) with one or repeated outcome measures (times: T_{hr} where $hr = 0$ for baseline, 0.5 to 12 post-infusion; peak cytokine concentration at T_2)¹², conducted with linear mixed models (LMM). The number of repeated measures varies by assessment. The key results are the main effects of sex, condition, and their interaction; for those analyses with repeated measures, the two main effects and interaction will further interact with the time variable. Other planned analyses include lagged (time series) relationships between cytokine outcomes and affect measures via general linear modeling (GLM). Standard pharmacokinetic parameters (e.g., AUC, C_{MAX} , T_{MAX}) may also be used to create summary cytokine and affect profile outcomes. Finally, covariates (i.e., pre-classification variables such as prior depression history, insomnia, or baseline CRP) will be tested if appropriate (i.e., $p < 0.15$) to assess the robustness of the results and further explicate the findings. **Aim 1** is tested with LMM for the following outcomes (timepoints): POMS Depression, DACL, Social Disconnection (T_0 , $T_1 - T_{12}$), Observer rated depression (T_0 , $T_{2,4,6,8,12}$), Cyberball Social Exclusion Task (T_2), Emotion Tasks (T_0 , T_2), Social Support Questionnaire (T_0 , T_2), Social Choice Task (T_0 , T_2), Reward Response (T_0 , T_2), Reward Learning (T_0 , T_2), and Reward Motivation (T_0 , T_2). The basic design for **Aim 2** is identical to Aim 1 but using age as the group variable (young females vs. older females) instead of sex. **Aim 3** is restricted to the endotoxin condition to examine the correlations between inflammatory responses and affective responses to endotoxin according to sex and age. These correlations will be examined using mixed-effects model linear regression, and cytokines and depressed mood, including excess negative affect and deficits in positive affect, will be entered in the regression models in their longitudinal format, thus reflecting all the measurements performed during the study (T_0 , $T_1 - T_{12}$). **Exploratory Aim** is tested using mixed-effects logistic regression, separately in the endotoxin and placebo groups, because the outcome (depressive episodes) is a binary variable repeatedly measured over 2 years. The predictor variables include the sum of POMS depression during 12 hours of experimental session, Cyberball Social Exclusion Task (T_2), Emotion Tasks (T_2), Social Choice Task (T_2), and Reward Tasks (Response, Learning, Motivation, Sensitivity) (T_2).

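### Baseline outcome values are screened by a sex difference at P<0.15 while T0 stays an unconstrained outcome row, so part of the precision available from baseline adjustment goes unused

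*Combined protocol and SAP*

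**What the plan says.** All of the analysis rules are in section C.2.8 of the combined protocol and SAP.

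- **Screen.** Pre-classification variables and baseline outcome values are compared by sex: "baseline values of outcomes will be compared; those that are significantly different between females and males" at P<0.15 "will be considered for inclusion as covariates in the main analyses". Passing the screen leads to consideration, not to automatic inclusion.
- **Balance tests.** "Adequacy of random assignment and matching will be tested using t-tests and chi-square tests as appropriate".
- **T0 as outcome.** The repeated measures are indexed from hour 0 (baseline), then "0.5 to 12 post-infusion; peak cytokine concentration at T_2". Of the 11 listed Aim 1 outcomes, 10 include T0. The exception is the Cyberball task, measured at T2 only.
- **Key results.** These are sex, condition and their interaction, each crossed with time where measures repeat. Aim 2 takes the same design with age group in place of sex.
- **Second use of the threshold.** "Finally, covariates (i.e., pre-classification variables such as prior depression history, insomnia, or baseline CRP) will be tested if appropriate" at p<0.15, as a robustness step. Baseline outcome values are not named there.

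The section does not commit to baseline adjustment, does not constrain T0 means, and does not say what happens to the T0 row if T0 also becomes a covariate. Section C.2.9 counts on matching and multivariate regression for the Aim 1 power, but names no covariate and gives no size for the gain. Section C.2.2 states that condition is randomised 1:1, stratified by sex.

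**The concern.** A baseline value is worth adjusting for because it predicts the later value. The screen asks instead whether the sexes differ at baseline. With no true sex difference, a baseline passes 15% of the time however prognostic it is.

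Meanwhile T0 is modelled as one more outcome time with free means in every cell. Randomisation within sex makes the endotoxin and placebo means equal at T0 in expectation. A model that estimates them separately gives up that knowledge and carries the T0 sampling error into the contrast. With 20 participants per cell, precision on the interaction is scarce and T0 is already collected.

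The rule also leaves the analyst free to choose, outcome by outcome and after seeing the data, whether baseline enters the model.

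**Working it through.** **Inputs from the documents.** 40 older females and 40 older males, randomised 1:1 within sex, so 20 per cell (C.2.2). Standardised effects are 0.51 in older females and 0.003 in older males, a difference of 0.507, with two-tailed alpha of 0.05 and stated power above 80% (C.2.9).

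**Assumed.** Correlation ρ between T0 and the post-infusion value; equal variance (SD 1) at both times; complete data.

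**1. The plan's own figure.**
- Simple 40 versus 40 comparison: SE = √(2/40) = 0.224; 0.507/0.224 = 2.27; power = Φ(2.27 − 1.96) ≈ 62%.
- Sex by condition interaction, post-infusion value only: SE = √(4/20) = 0.447; 0.507/0.447 = 1.134; power = Φ(1.134 − 1.960) ≈ 20%.

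Neither reaches 80%.

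**2. What the unconstrained T0 row estimates.** With complete data and free means for each cell at each time, the interaction of sex, condition and time (time t against T0) is the sex difference in the endotoxin-minus-placebo difference in mean change. Relative to a post-only analysis:
- change from T0: variance factor 2(1 − ρ);
- baseline adjustment: variance factor 1 − ρ²;
- efficiency of the first against the second: (1 − ρ²)/[2(1 − ρ)] = (1 + ρ)/2.

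**3. Numbers for one post-infusion time.** The SE is 0.447 times the square root of the factor.

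| ρ (assumed) | Change factor | Adjusted factor | Efficiency kept | Power, change | Power, adjusted |
|---|---|---|---|---|---|
| 0.3 | 1.40 | 0.91 | 65% | 16% | 22% |
| 0.5 | 1.00 | 0.75 | 75% | 20% | 26% |
| 0.7 | 0.60 | 0.51 | 85% | 31% | 36% |
| 0.9 | 0.20 | 0.19 | 95% | 72% | 74% |

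At ρ=0.5, for example, the adjusted SE is 0.447 × √0.75 = 0.387; 0.507/0.387 = 1.309; Φ(1.309 − 1.960) ≈ 26%.

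**4. What happens when the screen fires.** Suppose T0 is added as a time-constant covariate and the T0 row stays. The covariate contributes equally at T0 and at time t, so it cancels from the change. A random-intercept model fitted to one simulated data set (80 participants, four times, ρ=0.6) confirmed this: every three-way estimate was unchanged, with SE 0.405 both with and without the covariate. Only the time-constant sex by condition term moved (SE 0.461 to 0.320). Crossing the covariate with time did reduce the three-way SE, to 0.377, but the plan mentions no such term.

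**5. Does the screen distort inference?** In 20,000 simulated trials per scenario (ρ = 0.3, 0.5, 0.7; no true baseline sex difference), the screen switched from a change analysis to proper baseline adjustment whenever P<0.15. Under the null, type I error for the interaction was between 4.9% and 5.3% in every variant. Little precision was recovered: at ρ=0.5 the SE was 0.448 for change, 0.440 with the screen and 0.388 with adjustment always applied.

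**The case against.** The best defence is that baseline is not ignored. The T0 row stays in the model whether or not the screen fires, so change from T0 is always available. At high ρ this is nearly as good as adjustment. That stands, and it limits the point to a partial loss.

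Second, sex and age group are not randomised, so comparing them at baseline looks for confounding and is not a test of randomisation. Younger women are also recruited to be comparable with the older women on BMI, education and ethnicity (C.2.3), so checks of matching have a purpose. This stands too. The precision argument covers terms involving condition, and always adjusting for T0 would change what the sex or age main effect means.

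Third, the size depends on an assumed ρ and on one T2 contrast, whereas POMS, DACL and social disconnection are measured hourly. This is fair, but for those outcomes it can cut the other way. For the mean of 12 post-infusion times under compound symmetry at ρ=0.5, the variance factors are 0.542 for change and 0.292 for adjustment, a ratio of 1.86 against 1.33 at a single time.

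A reader might go further and infer that selecting covariates invalidates the standard errors, or that most models will be altered by chance. The documents do not support either reading. Simulated type I error stayed near 5%. Variables that pass are only considered for inclusion, so a pass rate is not a rate of changed models.

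**Conclusion.** The point holds as one of efficiency and prespecification. The screen uses a criterion unrelated to prognostic value. If it leads to T0 being added as a time-constant covariate beside the T0 row, the key interaction does not change. The rule therefore adds discretion without adding precision where it matters most.

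For the 10 outcomes with a T0, the planned contrast keeps 65% to 95% of the efficiency of baseline adjustment over ρ from 0.3 to 0.9. This assumes equal variances and complete data, and the documents give no ρ. It does not apply to Cyberball, which has no T0.

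A reader might infer that baseline adjustment would restore the stated Aim 1 power. It would not. To reach 80% on the interaction, the variance factor must fall to [0.507/(1.960 + 0.842)]²/0.20 ≈ 0.164, which needs ρ = √(1 − 0.164) ≈ 0.91. The power claim is a separate problem.

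**What to change.** - Delete the P<0.15 rule for baseline outcome values.
- For every outcome with a T0, keep T0 as an outcome row. Constrain the endotoxin and placebo means to be equal at T0 within each sex (Aim 1) or each age group (Aim 2). Leave T0 means free to differ between the sexes or age groups. Randomisation within those groups justifies the constraint, and the sex and age comparisons keep their meaning.
- If T0 is used as a fixed covariate instead, model post-baseline rows only, and state that the sex or age main effect is then conditional on baseline.
- Name the remaining confounders for the non-randomised sex and age comparisons in advance, in place of the P<0.15 selection. Descriptive comparison of those groups and checks of matching may stay.

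The cost is a change of wording in C.2.8. T0 is already collected, so no new data or visits are needed.

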The current study proposes to interrogate these mechanisms and how they differ as a function of sex and age. We will first leverage our ongoing experimental study examining endotoxin-induced depression in older adults (R01AG051944, PI [name]) to test for sex differences in endotoxin-induced alterations in negative and positive affective processes among older adults. This study is expected to recruit 160 subjects aged 60-80 years (80 females vs. 80 males). We next propose to recruit an additional 40 healthy premenopausal women (age 30-40) to participate in this supplemental study, which will allow us a complementary test of age as a vulnerability factor for endotoxin-induced depression and associated affective responding mechanisms in females. Specifically, in this randomized placebo-controlled experimental study, we aim to:

1. Examine the effect of female sex on affective responses to endotoxin in older adults. We hypothesize that, compared to males, females will present with higher negative affective responses and lower positive affective responses to endotoxin.

2. Examine the effect of age on affective responses to endotoxin in females. We hypothesize that, compared to older females, younger females will present with higher negative affective responses and lower positive affective responses to endotoxin.

3. Examine the correlation between inflammatory response and affective response to endotoxin according to sex and age. We hypothesize that the correlations between circulating proinflammatory cytokines and affective responses following endotoxin administration will be stronger in older females than in older males and in younger females than in older females.

Exploratory Aim: Examine the prospective associations between acute affective responses to endotoxin and long-term development of depressive disorders over 2 years, extending our preliminary findings.

RESEARCH STRATEGY

A. SIGNIFICANCE

A.1. Female Sex: A Vulnerability Factor for Inflammation-Induced Depression?

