
C.2.2. Overview of study design

To address Aim 1, examining sex differences in affective sensitivity to inflammation among older adults, we will select a total of 80 healthy older adults aged 60-80 years (40 males and 40 females), who are absent of current psychiatric illnesses, insomnia, and medical conditions (e.g., inflammatory disorders), into a placebo-controlled, randomized, double-blind, experimental inflammatory challenge protocol. Participants will be randomly assigned to receive either endotoxin (n=40) or placebo (n=40) in a between-subjects manner, stratified by sex. To address Aim 2, examining age differences in affective sensitivity to inflammation among females, we will recruit an additional 40 healthy premenopausal adult women (age 30-40) to be randomly assigned to receive endotoxin (n=20) or placebo (n=20).

For all participants, administration of endotoxin (0.8 ng/kg body weight vs. placebo), will be followed by self-report measures of depressed mood, negative and positive affect, and sickness symptoms (e.g., fatigue) assessed hourly over a 12-hour period; objective ratings of depressive symptoms by an observer blind to condition will be made every 2 hours. Behavioral tasks will be administered to coincide with peak onset of depressed mood, which we have previously shown to occur at 2 hours in both older and younger adults. Our prior protocol duration was 6 hours, but the current proposal will test for the presence of delayed termination of response^{57,58} and extend protocol duration to 12 hours. At baseline and starting two hours post-injection, at peak cytokine- and depressed mood responses, participants will complete the Probabilistic Reward Learning task⁵⁰⁻⁵², the Effort Expenditure for Reward Task,⁵⁹ the Social Choice task (i.e., intersection of reward

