In our endotoxin study of younger adults, the effect of endotoxin on depressed mood was large in females ($d=0.70$) while minimal in males ($d=0.003$).¹⁴ Among older adults, we expect to see a smaller but still substantial difference of effect between sexes. In our endotoxin study of older females (K23AG049085, PI [name]), as shown in C.1.1.3, the effect size of endotoxin on depressed mood was still large but expectedly smaller ($d=0.51$) than in younger females. For Aim 1, based on these estimates, the assumed minimal effect size in older males ($d=0.003$), and the use of matching and multivariate regression analyses, with 40 older healthy females and 40 older healthy males, we expect a power $>80\%$ ($\alpha=.05$, two-tailed). For Aim 2, assessing differences between younger and older females, our previous work with several of the behavioral reward tasks has yielded moderate effect sizes when assessing the relationship between increases in IL-6 and task performance (e.g., $f^2 = 0.22, 0.32$). Given this range of effect sizes, a multiple regression analysis with three predictors of interest (age, group, age x group interaction) and two covariates (BMI, education level) would require a sample size of 38 to 75 to detect effects with 0.80 power. This work has relied on very mild increases in IL-6, and we expect endotoxin to yield stronger effects. Indeed, prior work with the endotoxin model has shown significant differences on a reward motivation task with a sample of 29 participants (15 saline placebo, 14 endotoxin),⁹² and greater feelings of social disconnection following endotoxin vs. placebo were observed in a small sample of women ($n=20$; age 18-36) in our previous study. Thus, the current study aims to recruit 40 premenopausal women with equal randomization between the endotoxin and saline group, and an additional 40 females will be drawn from the parent study for a total sample of 80.

C.3. Interpretation of Results and Potential Concerns

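### Aims 1 and 2 are each tested on 11 outcomes with three key results and no lead test or multiplicity rule, and only the group-by-condition term answers the aims.

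*Combined protocol and SAP*

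**What the plan says.** The Specific Aims frame Aim 1 as a question about response: "Examine the effect of female sex on affective responses to endotoxin in older adults". The hypothesis covers two domains: "females will present with higher negative affective responses and lower positive affective responses to endotoxin". Aim 2 asks the same of younger against older women.

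C.2.8 sets out a two-by-two design (group by condition) fitted with linear mixed models. It states: "The key results are the main effects of sex, condition, and their interaction". For repeated measures, "the two main effects and interaction will further interact with the time variable". Aim 1 "is tested with LMM for the following outcomes (timepoints): POMS Depression, DACL, Social Disconnection" and eight further outcomes: observer-rated depression, Cyberball, emotion tasks, Social Support Questionnaire, Social Choice, and reward response, learning and motivation. The Aim 2 design "is identical to Aim 1 but using age as the group variable". AUC, Cmax and Tmax summaries are allowed as optional extras.

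No outcome, contrast or time is called primary for this study. The only mention of a primary outcome is in the quoted summary of the parent project (C.2.1). There is no multiplicity rule. C.2.8 gives no significance level for these tests; C.2.9 gives two-sided 0.05 in the Aim 1 power sentence. C.2.9 sizes Aim 1 on depressed mood and Aim 2 on reward tasks, and C.2.8 gives neither any special standing. C.2.2 treats the time of peak depressed mood as known, "which we have previously shown to occur at 2 hours in both older and younger adults".

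**The concern.** Two problems meet here. First, three terms share the status of key result, but only one bears on the aim. A sex difference present equally under endotoxin and placebo would give a significant group effect. An endotoxin effect of the same size in both sexes would give a significant condition effect. Neither shows that women respond differently, yet either could be reported as a key finding under Aim 1.

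Second, even the relevant interaction is tested on 11 outcomes per aim with nothing to say which one decides. Any one of them could be read as support, and the outcome used for sizing carries no more weight than the rest. The protocol says that a sex difference would direct priority for depression prevention towards older women (A.1, A.5), so these are inferential claims and not description alone.

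**Working it through.** **Inputs from the documents.** 11 outcomes per aim and three key results per outcome (C.2.8); two-sided 0.05 (C.2.9, Aim 1 only); 20 per cell (C.2.2); d = 0.51 in older women and an assumed 0.003 in older men (C.2.9). Correlations between outcomes and over time are not given and are assumed below.

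**The plan's own figure.** There is no stated family-wise error to reproduce. The related figure is Aim 1 power above 80%. For the interaction, the difference is 0.51 − 0.003 = 0.507 SD with SE = √(4/20) = 0.447. Power is Φ(0.507/0.447 − 1.96), about 20%. The stated figure is not reproduced for this contrast; about 123 per cell would be needed for 80%.

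**False positives, interaction tests only, per aim.**
- Independent outcomes: 1 − 0.95^11 = 43.1%.
- Equally correlated test statistics (simulation, 200,000 draws): 37% at 0.3, 30% at 0.5, 22% at 0.7, 13% at 0.9.
- If only the hypothesised direction counts: 24% when independent, 15% at 0.5.

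**Main effects read as support.** Suppose endotoxin raises one outcome by d = 0.51 in both sexes, with no sex effect and no interaction.
- Power for the condition effect at 40 v 40: Φ(0.51/√(2/40) − 1.96) = 63%.
- Chance that at least one of the three key results is significant: 1 − (1 − 0.626) × 0.95 × 0.95 = 66%, on one outcome, with no sex difference in response.

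**Time, for the hourly scales.** POMS Depression, DACL and Social Disconnection are measured at T0 and T1–T12, 13 times. A two-way term averaged over these keeps a fraction of the peak equal to the mean of the response profile. T0 adds a zero to that mean.
- Assumed profile 0, 0.5, 1, 0.8, 0.5, 0.25, 0.1, then 0 from 7 h: 3.15/13 = 24% of peak.
- Assumed slower recoveries: 42% to 53% of peak.

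Treating 0.507 SD as a T2 effect, with constant correlation 0.5 over time, the variance of the averaged contrast is (4/20) × (1 + 12 × 0.5)/13 = 0.108, so SE = 0.328. Power for the average is 7% on the fast profile and 10% to 13% on the slower ones. The planned group-by-condition-by-time test with 12 df has 18.5% on the fast profile. T2 adjusted for T0 has SE = √(0.2 × (1 − 0.5²)) = 0.387 and power 26%. At correlation 0.7 the last two become 31% and 35%.

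**The case against.** Reporting main effects beside an interaction is normal factorial practice, and nothing in the plan says that a main effect counts as support. C.2.9 also speaks of a difference in effect between the sexes, which is the interaction. That is fair as to intent, but C.2.8 gives the three terms equal status, and the SAP is where that should be settled.

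Several stronger readings are tempting, and the documents do not support them:

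- *A false claim is more likely than not.* On interaction tests the figure is at most 43% per aim, and the mood scales are surely correlated. Counting all 33 key results gives 1 − 0.95^33 = 82% under independence. That treats every main effect as both null and as support, whereas the condition effect is probably real.
- *68% over both aims.* 1 − 0.95^22 ignores the 40 older women used in both. Allowing for them gives 65% if outcomes are independent and 49% at correlation 0.5.
- *Everything is tested at 0.05.* That level is written for Aim 1 power only.
- *Averaging cuts power from 26% to 7%.* This rests on an assumed recovery by 7 h, while C.2.2 and C.2.4 extend the session to 12 h because the response may end late. It also omits the planned time interaction (18.5%). Nor do the documents say that d = 0.51 is a 2-hour effect; if it is a session average in its own SD, power is about 20%.
- *The slope would have the wrong sign.* This needs a linear time trend, which the plan does not propose.
- *No time is fixed.* Seven of the 11 outcomes have T2 as their only post-infusion time. The gap concerns the three hourly scales and observer-rated depression.

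Requiring success in both affect domains would cut the error sharply: with seven negative and four positive outcomes, (1 − 0.95^7) × (1 − 0.95^4) = 0.302 × 0.185, about 6%. The hypothesis wording could be read that way, but no such rule is stated.

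**Conclusion.** The concern holds in a limited form. Each of Aims 1 and 2 has 11 outcomes, three key results per outcome, no lead test and no multiplicity control, and two of the three key results do not address the aim. The chance of at least one false interaction per aim is 43% under independence and roughly 22% to 30% at correlations of 0.5 to 0.7. These figures assume testing at 0.05, and the correlations are assumptions. Even the lower ones are more than four times 5%.

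For the hourly scales, the two-way term dilutes a response that peaks at 2 hours because it includes the pre-infusion value and later hours. The direction is clear. The size is not, because the recovery profile is unknown.

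This is something the sponsor should correct, and it goes beyond missing detail: followed as written, the plan lets results that do not test the aim stand as key findings.

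**What to change.** In C.2.8:

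1. Make group-by-condition the sole key contrast for each aim, and report the group and condition main effects descriptively.
2. Name a lead outcome per aim from the sponsor's own sizing basis. For Aim 1: POMS Depression at T2 adjusted for T0, with time categorical. For Aim 2: either the same, or one named reward-task outcome at T2 adjusted for T0, since C.2.9 sized that aim on reward tasks.
3. State the test level for both aims. With one lead test per aim at 0.05, the error is 5% per aim and about 1 − 0.95² = 9.75% for either aim if the two tests are independent.
4. Treat the other outcomes as secondary, with Holm adjustment within a negative-affect and a positive-affect family.
5. POMS Depression alone leaves the positive-affect half of the hypothesis without a lead test. If both domains are meant to support the aim, name one lead outcome in each and say whether both must succeed or alpha is split.

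The cost is SAP wording and a stricter threshold for secondary outcomes. With POMS Depression as the lead, the smallest p-value would need to reach 0.05/6 = 0.0083 among six negative-affect outcomes and 0.05/4 = 0.0125 among four positive-affect ones. No new data or participants are needed. The change does not raise the roughly 20% power of the Aim 1 interaction (26% at T2 adjusted for T0, if that correlation is 0.5), so the power statement in C.2.9 needs separate attention.

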Inflammatory Cytokine, Signaling Pathway, Gene Expression Analysis: Blood samples will be collected at baseline, every half hour for the first two hours, and hourly for the remainder of the 12 h. Samples will be immediately processed and stored at -80°C. Plasma samples (all timepoints) will be assayed for pro- and anti-inflammatory cytokines (IL-1, IL-6, IL-8, TNF, and IL-10) by means of a high sensitivity bead-based multiplex immunoassay (Performance High Sensitivity Human Cytokine, R& D Systems, Minneapolis, MN) and a Bio-Plex 200 (Luminex) Instrument, with excellent intra- and inter-assay reproducibility⁹⁷ and very strong correlations ($r \geq 0.94$) with high sensitivity ELISA.⁹⁸ We are examining IL-1 β , TNF, and IL-6 as these cytokines are increased in response to endotoxin and correlate with increases in depressed mood. IL-8 is also assayed because endotoxin activates the TLR-4 receptor and IL-8 is a proinflammatory cytokine that is released with TLR-4 activation. We also explore changes in IL-10, an anti-inflammatory cytokine that is thought to counter-regulate the inflammatory responses; no study has examined IL-10 responses to endotoxin and determined whether its expression might alter magnitude/duration of inflammatory response. Baseline levels of CRP will be assessed, as CRP is a robust marker of systemic inflammation. Baseline levels of CRP may moderate increases in inflammation and affective responding. However, repeated measures of CRP will not be obtained. Increases in IL-6 induce CRP over several hours or longer; hence, the experimental protocol is too short in duration to evaluate changes in CRP. Peripheral blood mononuclear cell (PBMC) nuclear extracts (baseline, 30 min, 1 h, 2 h or peak cytokine response) will be prepared and assayed to quantify the amount of activated NF- κ B p65 present in the nucleus utilizing recombinant p65 (Active Motif, Carlsbad, CA) as the reference

standard (range 0.08-5.00ng),⁹⁹ as we have previously described.¹⁰⁰ At baseline, 2- and 4 hours post-injection, blood samples will be drawn in PaxGene RNA tubes, which preserve RNA integrity. Expression of genes involved in proinflammatory pathways (*IL1B*, *IL6*, *IL8*, *CD83*, *CCL3*, *TNFAIP3*, and *NF-κB/Rel family*) will be assayed by quantitative real-time RT-PCR using established TaqMan Gene Expression Assays. Genome-wide transcriptional profiling will be performed using Illumina HT-12 BeadArrays.

C.2.7. Two-Year Longitudinal Follow-up

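### The lagged cytokine–affect analyses are assigned to a general linear model with no stated handling of within-person correlation; if person-hours are treated as independent, false positives exceed 5%

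*Combined protocol and SAP*

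**What the plan says.** All the modelling text is in section C.2.8.

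- **Aims 1 and 2:** group-by-condition designs, with repeated outcomes "conducted with linear mixed models (LMM").
- **Aim 3**, the main cytokine–affect test, endotoxin condition only: "These correlations will be examined using mixed-effects model linear regression".
- **Exploratory aim:** mixed-effects logistic regression, chosen because the binary outcome is measured repeatedly.
- **Lagged analyses:** "Other planned analyses include lagged (time series) relationships between cytokine outcomes and affect measures via general linear modeling (GLM"). Nothing more is said about lag, rows, covariance or standard errors.
- **Summary outcomes:** the following sentence says that AUC, Cmax and Tmax "may also be used to create summary cytokine and affect profile outcomes".
- **Missing data:** "missing data will not be imputed as the methods selected allow for missing data under common missingness assumptions".

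On the schedule, C.2.2 has self-reported affect "assessed hourly over a 12-hour period". For cytokines, C.2.6 states: "Blood samples will be collected at baseline, every half hour for the first two hours, and hourly for the remainder of the 12 h".

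The section also uses a GLM for transcript abundance. That analysis has a different outcome and is not part of this point.

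**The concern.** Repeated hourly values from one person resemble each other, and neighbouring hours more so. When both the predictor and the outcome behave this way, a model that counts each person-hour as a separate observation understates the standard error of the slope. A lead–lag association would then be declared too often when none exists.

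Three further matters bear on the choice of model.

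- **Repeated-measures GLM.** It has no natural place for a predictor that changes every hour. In its usual complete-case form it drops anyone with a missing hour, which would conflict with the plan's missing-data statement.
- **A single pooled slope.** It mixes differences between people (those with higher cytokines feel worse) with change within a person over time. Only the second is a lagged effect.
- **Shared time course.** The plan places peak cytokine concentration (C.2.8) and peak depressed mood (C.2.2) both at about two hours. Without a term for hour, that shared time course could by itself produce a lagged slope.

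At stake is the reading of any reported temporal ordering between cytokines and mood.

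**Working it through.** The documents give no error rate, power or sample size for the lagged analyses, so there is no planned figure to reproduce. The check asks what each form of GLM would do.

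**Inputs from the documents**
- Affect: T0 and T1–T12, so 13 values per person.
- Cytokines: 0, 0.5, 1, 1.5 and 2 h, then 3–12 h, so 15 values, of which 13 fall on the hour.
- Lag 1 on the hour: m = 12 pairs per person.
- Persons: "Participants will be randomly assigned to receive either endotoxin (n=40) or placebo (n=40) in a between-subjects manner, stratified by sex"; 40 persons give 40 × 12 = 480 rows.

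**Assumptions**
- Two-sided α = 0.05. C.2.9 states this for Aim 1 only.
- Lag of one hour, and unrelated cytokine and affect series with the same correlation structure in both.
- ICC and autocorrelation are varied, because none is reported.

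**Formula for pooled rows.** With correlation ρ_k between values k hours apart in each series, the slope variance is inflated by

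D = 1 + 2 Σ_{k=1..11} (1 − k/12) ρ_k²

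and the true type I error is 2[1 − Φ(1.96/√D)]. The number of persons cancels, so a larger sample does not help.

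**Exchangeable correlation** (ρ_k = ICC, so D = 1 + 11·ICC²)

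| ICC | D | Type I error |
|---|---|---|
| 0.1 | 1.11 | 6% |
| 0.3 | 1.99 | 17% |
| 0.5 | 3.75 | 31% |
| 0.9 | 9.91 | 53% |

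**AR(1) correlation** (ρ_k = r^k)

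| r | D | Type I error |
|---|---|---|
| 0.3 | 1.18 | 7% |
| 0.5 | 1.59 | 12% |
| 0.7 | 2.61 | 23% |
| 0.9 | 6.09 | 43% |

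**Person effect plus AR(1)** (ρ_k = ICC + (1 − ICC)·r^k). The simulations use 40 persons and remove hour means. The mixed model is the one proposed under the fix.

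| ICC / r | Lag-1 correlation | D | Formula | Pooled GLM, simulated | Mixed model, simulated |
|---|---|---|---|---|---|
| 0.1 / 0.3 | 0.37 | 1.39 | 10% | 10% | 5% |
| 0.3 / 0.3 | 0.51 | 2.40 | 21% | 20% | 5% |
| 0.5 / 0.5 | 0.75 | 4.73 | 37% | 36% | 5% |
| 0.6 / 0.3 | 0.72 | 5.35 | 40% | 39% | 5% |

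Each simulated rate in this table comes from 1,000 null data sets. Other runs of the same settings put the pooled rates within a few points of these and the mixed model at about 4–6%. At 0.5/0.5, pooled rates with 20, 40 and 60 persons were 37.0%, 37.2% and 39.8%.

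**What 20–40% requires.** Setting the error to 20% gives D = (1.960/1.282)² = 2.34, and 40% gives D = (1.960/0.842)² = 5.42. With exchangeable correlation, ICC = √[(D − 1)/11], which is 0.35 to 0.63 in both series. Under pure AR(1), r of about 0.7 to 0.9 is needed.

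**Other forms of GLM, same null data, 40 persons**
- Across persons at a single lag pair: about 4–6%.
- One mean (AUC-like) value per person: about 4–6%.
- Pooled rows with person-clustered standard errors: about 5–8%.
- Person fixed effects: about 4–6% under exchangeable correlation, but 10–28% under AR(1) of 0.5–0.9.
- Previous affect value as a covariate: about 5–6% under AR(1), but up to about 13% under exchangeable correlation.

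**The case against.** The strongest reply is that the plan never says that person-hours are pooled. GLM is a broad term. It could mean a regression across persons from one chosen hour to a later one, or a model of the AUC, Cmax and Tmax summaries named in the next sentence. Both keep about 5%. The missing-data conflict arises only if a repeated-measures GLM is meant. With weak dependence even the pooled version is close to nominal: 6% at ICC 0.1 and 7% at AR(1) 0.3. Clustered standard errors would also largely repair a pooled GLM.

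All of this stands, and it is why the rate has to be conditional. It does not remove the point. The description of these analyses as time series indicates the hourly data, while the summary outcomes are a separate and optional item. The forms of GLM that hold 5% without special standard errors compare people with one another, so they do not show that a person's cytokine change comes before that person's mood change. Clustered standard errors do not separate the two components either.

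A reader might also infer that these analyses carry the trial's case that inflammation precedes mood change. The documents do not support that. No aim or hypothesis in the Specific Aims concerns temporal order, the lagged work is listed among other planned analyses, and Aim 3 already uses a mixed model.

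**Conclusion.** The point holds in a conditional form. For a secondary analysis of densely repeated data, the plan names a less suitable model than the one it uses for its aims, and does not say how within-person correlation would be handled. If person-hours are treated as independent, the false-positive rate is about 20–40% for moderate correlation (exchangeable ICC of about 0.35–0.63 in both series) and about 6% to over 50% across the plausible range. These figures rest on assumed correlations, a one-hour lag and equal correlation in the two series.

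It would be tempting to conclude that the lagged analyses will have a 20–40% error rate. The documents do not support that, because they specify neither pooled rows nor any correlation. Aim 3 is unaffected. The change is worth making before analysis, but the trial's main conclusions do not depend on it.

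**What to change.** In C.2.8, replace the GLM for the lagged analyses with the linear mixed model that the plan already uses for repeated outcomes:

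- participant random intercept and AR(1) residuals;
- hour as a factor;
- lagged cytokine entered as two terms, the person's mean and the hourly deviation from it;
- the lag or lags stated in advance, with the within-person term as the test.

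The serial-correlation term should not be left out, since person fixed effects alone gave 10–28% under AR(1) of 0.5–0.9. The model can use people with some missing hours, in keeping with the plan's missing-data statement. If an across-person or per-person-summary GLM is what was intended, the plan should say so and describe the result as a between-person association.

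The cost is about one sentence in the plan, with no new data. Standard errors will be wider than a pooled GLM would give.
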